6.5 Early Termination Visit and Withdrawal Procedures

The end of treatment for patients completing the study is the Day 85 visit. For patients who are withdrawn from the study prior to completion, all Day 85 procedures will be performed at an early termination visit. These procedures include the following:

- Perform full physical examination.
- Record vital signs and weight.
- Collect urine sample for urinalysis assessment.

- Perform urine pregnancy test.
- Collect blood samples for clinical safety chemistry panel, coagulation, and hematology assessments.
- Collect blood samples for fasting lipid panel assessment.
- Collect blood samples for fasting apolipoproteins and LDL-C (beta-quant).
- Collect blood samples for hsCRP, PCSK9, and fibrinogen analysis.
- Collect blood samples for anti-drug antibody analysis
- Collect blood samples for sparse PK, cytokine panel and complement activation analysis.
- Perform 12-lead ECG measurements.
- Record adverse events.
- Record concomitant medications.

7 EFFICACY ASSESSMENTS

7.1 Primary Endpoints

The primary safety/tolerability endpoints for this study are as follows:

- incidence and severity of any drug-related AE
- incidence of clinically significant laboratory abnormalities, based on drug-induced changes from baseline in hematology, clinical safety chemistry, and urinalysis test results.

7.2 Secondary Endpoints

The secondary efficacy endpoints include the following changes from baseline measured approximately 28 days after the first and 28 and 56 days after the last injection of study drug:

• The percent change in PCSK9 and LDL-C

7.3 Exploratory Endpoints

The exploratory endpoints include the following:

PD endpoints are the absolute and % changes from baseline (except where indicated) in the levels of the following in serum or plasma over the time course of the treatment period and follow-up:

- PCSK9 (absolute only)
- LDL-C (absolute only)
- VLDL-C
- triglycerides
- HDL-C
- Non-HDL-C
- total cholesterol
- lipoprotein (a)
- apolipoproteins B and A-I
- hsCRP

The following PK parameters will be calculated for CIVI 007, where possible:

- C_{max}
- time of the maximum observed plasma concentration (t_{max})
- Area under the plasma concentration-time curve from time 0 to the time of last quantifiable concentration (AUC_{0-t})
- concentration observed at pre-dose (C_{trough})

Additional exploratory PK parameters, which may include but are not limited to the following, may be calculated:

- area under the plasma concentration-time curve from time 0 extrapolated to infinity $(AUC_{0-\infty})$
- area under the plasma concentration-time curve from time 0 to 24 hours (AUC₀₋₂₄)
- area under the plasma concentration-time curve from time 0 to 48 hours (AUC₀₋₄₈)
- percentage of AUC_{0-∞} that is due to extrapolation (%AUC_{extrap})
- apparent termination elimination rate constant (λ_z)
- apparent plasma terminal elimination half-life $(t_{1/2})$
- apparent total plasma clearance (CL/F)
- apparent volume of distribution during the terminal phase (V_z/F)

7.4 Pharmacokinetics

Sparse PK sampling will be conducted for all consenting participants. Sampling will be performed on dosing days, and at each study visit during the Treatment and Follow-up Periods. For each of the dosing days, a PK sample will be drawn pre-dose (- 1 hour), 3 hours (±1 hour) post-dose, and at 8 hours (±1 hour) post-dose.

The population PK model created based on data from the ongoing Phase 1 study will be refined to evaluate the relationship of CIVI 007 PK to demographics and background statin therapy. The model will be periodically refined as new and broader datasets emerge to include the covariates of special populations, concomitant medications, and disease state.

8 SAFETY ASSESSMENTS

The safety variables include adverse events, safety laboratory parameters (including clinical safety chemistry, hematology, coagulation parameters including fibrinogen, complement activation, cytokines, and urinalysis), 12-lead ECGs, physical examinations, and vital signs. Samples will also be collected for the potential future assessment of anti-drug antibodies.

8.1 Individual Patient Safety Monitoring and Criteria For Discontinuation of Study Drug

When any the following criteria are met, patients will be monitored for safety and discontinuation of study drug considered using the following guidance.

- Liver (as per FDA guidance on drug-induced liver injury 16)
 - Patients with signs or symptoms consistent with liver injury (such as nausea, vomiting, anorexia, fatigue, right upper abdominal pain or discomfort) should undergo immediate testing of ALT, AST, GGT, bilirubin, ALP, PT, and INR.
 - In the absence of clinical symptoms, patients with ALT or AST > 3xULN (if normal at baseline) or >2-fold change (if abnormal at baseline) should be retested within 48 to 72 hours for the usual serum measures (ALT, AST, ALP, and bilirubin) to confirm the abnormalities and to determine if they are increasing or decreasing. There also should be inquiry made about symptoms at the time of follow-up.
 - If the above abnormalities are confirmed,
 - repeat liver enzyme and serum bilirubin tests two or three times weekly. The frequency of retesting can decrease to once a week or less if abnormalities stabilize or the study drug has been discontinued and the patient is asymptomatic.
 - Obtain a more detailed history of symptoms and prior or concurrent diseases.
 - Obtain a history of concomitant drug use (including nonprescription medications and herbal and dietary supplement preparations), alcohol use, recreational drug use, and special diets.
 - Rule out acute viral hepatitis types A, B, C, D, and E; autoimmune or alcoholic hepatitis; NASH; hypoxic/ischemic hepatopathy; and biliary tract disease.
 - Obtain a history of exposure to environmental chemical agents.
 - Obtain additional tests to evaluate liver function, as appropriate (e.g., INR, direct bilirubin).
 - Considering gastroenterology or hepatology consultations.
 - Study drug discontinuation should occur if:
 - ALT or AST >8xULN
 - ALT or AST >5xULN for more than 2 weeks
 - ALT or AST >3xULN and (bilirubin >2xULN or INR >1.5)
 - ALT or AST >3xULN with the appearance of fatigue, nausea, vomiting, right upper quadrant pain or tenderness, fever, rash, and/or eosinophilia (>5%)
- Platelet Count

- Patients whose platelet count decreases to <140,000 mm³ should begin weekly platelet monitoring, and patient whose platelet count decreases to <75,000 mm³ should have platelets monitored every 2 to 3 days. Patients whose platelet count decreases to <50,000 mm³ should discontinue drug and undergo daily platelet monitoring; consultation with a hematologist is also recommended.

Renal

- Patients with concern for renal toxicity, spot urine UPCR and/or spot UACR should be obtained. Patients with UPCR >50% from baseline or 1.5x ULN should be monitored at least every 2 weeks.
- Study drug should be discontinued if patients experience an unexplained, confirmed increase in serum creatinine of 0.3 mg/dL above baseline; unexplained, confirmed 25% decline in eGFR from baseline; or new-onset hematuria, albuminuria (UACR ≥250 mg/g), or proteinuria (≥UPCR 500 mg/g) confirmed on repeat testing.

8.2 Adverse Events

An adverse event is defined as any untoward medical occurrence in a clinical investigation patient administered a pharmaceutical product, which does not necessarily have a causal relationship with this treatment. An adverse event can therefore be any unfavorable and/or unintended sign (including an abnormal laboratory finding), symptom, or disease temporally associated with the use of an IMP, whether or not related to the IMP. All adverse events, including observed or volunteered problems, complaints, or symptoms, are to be recorded on the appropriate eCRF.

Adverse events, which include clinical laboratory test variables, will be monitored and documented from the time of screening until completion of the Day 85 Visit, early termination visit or extended Follow-up, whichever is later. Patients should be instructed to report any adverse event that they experience to the Investigator, whether or not they think the event is due to study treatment. Beginning at screening, Investigators should make an assessment for adverse events at each visit and record the event on the appropriate adverse event eCRF.

Wherever possible, a specific disease or syndrome rather than individual associated signs and symptoms should be identified by the Investigator and recorded on the eCRF. However, if an observed or reported sign or symptom is not considered a component of a specific disease or syndrome by the Investigator, it should be recorded as a separate adverse event on the eCRF. Additionally, the condition that led to a medical or surgical procedure (e.g., surgery, endoscopy, tooth extraction, or transfusion) should be recorded as an adverse event, not the procedure itself.

Any medical condition already present at Screening, should be recorded as medical history and not be reported as an adverse event unless the medical condition or signs or symptoms present at baseline changes in severity, frequency, or seriousness at any time during the study. In this case, it should be reported as an adverse event.

Clinically significant abnormal laboratory or other examination (e.g., ECG) findings that are detected during the study or are present at Screening, and significantly worsen during the study should be reported as adverse events, as described below. The Investigator will exercise his or her medical and scientific judgment in deciding whether an abnormal laboratory finding or other abnormal assessment is clinically significant. Clinically significant abnormal laboratory values occurring during the clinical study will be followed until repeat tests return to normal, stabilize, or are no longer clinically significant. Abnormal test results that are determined to be an error should

not be reported as an adverse event. Laboratory abnormalities or other abnormal clinical findings (e.g., ECG abnormalities) should be reported as an adverse event if any of the following are applicable:

- If an intervention is required as a result of the abnormality
- If action taken with the study drug is required as a result of the abnormality
- Based on the clinical judgment of the Investigator

8.2.1 Adverse (Drug) Reaction

All noxious and unintended responses to a medicinal product related to any dose should be considered an adverse drug reaction. "Responses" to a medicinal product means that a causal relationship between a medicinal product and an adverse event is at least a reasonable possibility, i.e., the relationship cannot be ruled out.

8.2.2 Unexpected Adverse Drug Reaction

An Unexpected Adverse Drug Reaction is defined as an adverse reaction, the nature or severity of which is not consistent with the applicable product information. For CIVI 007 the reference safety information is included in the IB currently in force. The reference safety information will be reviewed yearly and the periodicity of the review will be harmonized with the reporting period of the Development Safety Update Report.

8.2.3 Assessment of Adverse Events by the Investigator

The Investigator will assess the severity (intensity) of each adverse event as mild, moderate, or severe, and will also categorize each adverse event as to its potential relationship to study drug using the categories of yes or no.

Assessment of severity:

Mild – An event that is easily tolerated and generally not interfering with normal daily activities.

Moderate – An event that is sufficiently discomforting to interfere with normal daily activities.

Severe – An event that is incapacitating with inability to work or perform normal daily activities.

Causality assessment:

The relationship of an adverse event to the administration of the study drug is to be assessed according to the following definitions:

No (unrelated, not related, unlikely to be related) – The time course between the administration of study drug and the occurrence or worsening of the adverse event rules out a causal relationship and another cause (concomitant drugs, therapies, complications, etc.) is suspected.

Yes (possibly, probably, or definitely related) – The time course between the administration of study drug and the occurrence or worsening of the adverse event is consistent with a causal relationship and no other cause (concomitant drugs, therapies, complications, etc.) can be identified.

The definition implies a reasonable possibility of a causal relationship between the event and the study drug. This means that there are facts (evidence) or arguments to suggest a causal relationship.

The following factors should also be considered:

• The temporal sequence from study drug administration-

The event should occur after the study drug is given. The length of time from study drug exposure to event should be evaluated in the clinical context of the event.

• Underlying, concomitant, intercurrent diseases-

Each report should be evaluated in the context of the natural history and course of the disease being treated and any other disease the patient may have.

Concomitant drug-

The other drugs the patient is taking or the treatment the patient receives should be examined to determine whether any of them might be recognized to cause the event in question.

• Known response pattern for this class of study drug-

Clinical and/or preclinical data may indicate whether a particular response is likely to be a class effect.

Exposure to physical and/or mental stresses-

The exposure to stress might induce adverse changes in the recipient and provide a logical and better explanation for the event.

• The pharmacology and PK of the study drug-

The known pharmacologic properties (absorption, distribution, metabolism, and excretion) of the study drug should be considered.

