5.2 Rationale for Dosing

Standard antisense molecules have been demonstrated to scale allometrically between the mouse, monkey, and human based on body weight. Accordingly, with a NOAEL in monkeys of 30 mg/kg, the doses of and an average body weight of 60 kg) is > CCI - fold below the NOAEL.

More importantly, based on initial data from the ongoing FIH study and within the context of a limited experience, CIVI 007 appears to provide the expected pharmacologic profile associated with PCSK9 inhibition. CIVI 007 shows PCSK9 knockdown that begins around 12.5 mg with maximal inhibition of approximately 90% at mg. The efficacy profile includes robust, dosedependent reductions in atherogenic lipoproteins and lipids that begin within 1 week of administration and are stable out to 4 weeks after administration. Changes in lipoproteins and lipids after multiple doses are consistent with those after single doses.

There were no obvious drug-related safety findings in the dose range of 12.5 to a mg. Grade 1 ALT elevations appeared in both placebo and active doses with similar frequency. At higher doses, and based on higher levels of ALT increase, a signal of hepatotoxicity was apparent at 300 mg with a potential signal in one subject at 150 mg that was confounded with alcohol intake at the time of liver testing.

CIVI 007 therefore appears to have a favorable clinical profile at lower doses and these justify advancement to Phase 2a testing in this study.

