9.2.3 Interim Analysis

No formal interim analyses are planned for this study other than descriptive analyses required for the SRC to review accumulating safety information. Interim safety reviews and lipid analyses (sponsor only) will initially occur when approximately 12 patients have received their first study drug injection and have two weeks of follow-up data available. Subsequent analyses will occur with the accrual of each 12 new patients who have two week follow-up data available with a final review when the last 12 patients have two week follow-up data available.

Guidelines for interim study stoppage by the SRC will be based on safety parameters and the cumulative evidence of treatment group imbalances as follows:

- Clinically relevant signs or symptoms of similar nature occur in 3 or more patients in a treatment group that, in the opinion of the Investigator, warrants stopping based on concerns of patient safety.
- Two or more patients experiencing a non-cardiovascular SAE or 4 or more patients experience severe AEs.
- There is evidence of clinically significant increases in the following:
 - liver tests, defined as 3 × ULN (confirmed with repeat testing) in either ALT or AST; or 2 × ULN in either ALP or bilirubin, in 3 or more patients in a treatment group.
 - o confirmed platelet count decreases to <140,000 mm³
 - o confirmed increases in serum creatinine of 0.3 mg/dL above baseline

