# 3.6.1 Adverse Events (AEs)

AEs will be monitored and documented from the time of screening until completion of the Day 85 Visit, early termination visit or extended Follow-up, whichever is later. All AEs will be coded to system organ class and preferred term using MedDRA terminology version 22.0 (or the most recent version available).

Treatment-emergent adverse events (TEAEs) are defined as AEs that worsen in severity or relationship to study drug or start on or after the time of start of first study drug administration.

Adverse events of special interest (AESIs) include CTCAE Version 5.0 Grade 2 or higher ALT measurements, and injection site reactions (ISRs).

An overview of AEs will be provided including counts and percentages of patients (and event counts) with the following:

• Any AEs (overall and by maximum severity)

- Any drug related AEs (overall and by maximum severity)
- Any AEs of special interest (ALT and injection site reactions)
- Any serious AEs (SAEs)
- Any AEs leading to discontinuation of study treatment
- Any AEs leading to discontinuation of study
- Any AEs leading to death

The primary endpoint is the incidence and severity of any drug-related AEs. The number and percentage of patients who experience 1 or more drug-related (possibly, probably, or definitely related) AEs will be presented by system organ class and preferred term by overall and by maximum severity. In addition, summaries will be provided by system organ class, preferred term, and maximum severity.

Listings of patients with drug-related AEs will be presented.

Counts and percentages of patients (and event counts) will also be presented by system organ class and preferred term for each of the categories in the overview.

Listings will be presented for all AEs, specifically for AESIs, SAEs and AEs leading to death.

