#### 3.6.2 Clinical Laboratory Tests

Clinical safety chemistry, hematology, coagulation, and urinalysis will be collected at each study visit. Fibrinogen, cytokine and complement activation sampling will be collected at Day 1, Day 8, Day 15, Day 22, Day 29, Day 36, Day 43, Day 57 and Day 85 or early termination. hsCRP will be collected at Day 1, Day 8, Day 15, Day 22, Day 29, Day 36, Day 43, Day 57 and Day 85 or early termination. Thyroid-stimulating hormone (TSH), hemoglobin A1c (HbA1c), and serology will be collected in the Screening Visit.

Observed values and changes from baseline will be presented at each scheduled visit and baseline by laboratory test.

The primary endpoint is the incidence of clinically significant laboratory abnormalities, based on changes from baseline in hematology, clinical safety chemistry, and urinalysis test results. The incidence of abnormalities will be summarized with counts and percentages of patients for selected parameters grading by Common Terminology Criteria for Adverse Events (CTCAE) Version 5.0 if appropriate.

Laboratory	CTCAE Term	Grade 1	Grade 2	Grade 3	Grade 4
Chemistry	Alanine aminotransferase increased	>ULN - 3.0 x ULN if baseline was normal;	>3.0 - 5.0 x ULN if baseline was normal;	>5.0 - 20.0 x ULN if baseline was normal;	>20.0 x ULN if baseline was normal;
		1.5 - 3.0 x baseline if baseline was abnormal	>3.0 - 5.0 x baseline if baseline was abnormal	>5.0 - 20.0 x baseline if baseline was abnormal	>20.0 x baseline if baseline was abnormal
	Aspartate aminotransferase increased	>ULN - 3.0 x ULN if baseline was normal;	>3.0 - 5.0 x ULN if baseline was normal;	>5.0 - 20.0 x ULN if baseline was normal;	>20.0 x ULN if baseline was normal;
		1.5 - 3.0 x baseline if baseline was abnormal	>3.0 - 5.0 x baseline if baseline was abnormal	>5.0 - 20.0 x baseline if baseline was abnormal	>20.0 x baseline if baseline was abnormal

Laboratory	CTCAE Term	Grade 1	Grade 2	Grade 3	Grade 4
	Blood bilirubin	Total Bilirubin	Total Bilirubin	Total Bilirubin	Total Bilirubin
	increased	>ULN - 1.5 x ULN if baseline was normal;	>1.5 - 3.0 x ULN if baseline was normal;	>3.0 - 10.0 x ULN if baseline was normal;	>10.0 x ULN if baseline was normal;
		> 1.0 - 1.5 x baseline if baseline was abnormal	>1.5 - 3.0 x baseline if baseline was abnormal	>3.0 - 10.0 x baseline if baseline was abnormal	>10.0 x baseline if baseline was abnormal

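### AE severity is rated only by effect on daily activities, so a symptom-free laboratory AE that stops study drug is Mild in one primary endpoint and CTCAE Grade 3 in the other

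*Protocol*

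**What the plan says.** Protocol 8.2.3 sets one scale for all events: "The Investigator will assess the severity (intensity) of each adverse event as mild, moderate, or severe". The bottom level is "Mild – An event that is easily tolerated and generally not interfering with normal daily activities" and the top level is "Severe – An event that is incapacitating with inability to work or perform normal daily activities". The middle level also turns on discomfort and daily activities.

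Protocol 8.2 defines an AE as "any unfavorable and/or unintended sign (including an abnormal laboratory finding), symptom, or disease". It asks for a laboratory abnormality to be reported as an AE when it needs an intervention, when it leads to action on study drug, or when the investigator judges that it should be. Section 8.1 has guidance for liver enzyme rises without symptoms. Only one of its four liver criteria for stopping drug depends on symptoms, signs or eosinophilia; ALT or AST above 8 × ULN is enough by itself.

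The first primary endpoint (Protocol 7.1, SAP 2.3.1) is the incidence and severity of drug-related AEs. SAP 3.6.1 carries the severity rating into the overview, "Any drug related AEs (overall and by maximum severity", and into the tables by system organ class and preferred term. The second primary endpoint is clinically significant laboratory abnormalities. For this, SAP 3.6.2 uses CTCAE Version 5.0, in which ALT ">5.0 - 20.0 x ULN if baseline was normal" is Grade 3.

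Protocol 9.2.3 includes a stoppage guideline of "4 or more patients experience severe AEs". On the drug itself, Protocol 5.2 reports that in the first-in-human study "a signal of hepatotoxicity was apparent at 300 mg", with a possible signal in one subject at 150 mg.

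**The concern.** The liver signal is the known toxicity of this drug, and Protocol 8.1 expects that enzyme rises may come without symptoms. For such an event, the severity part of the first primary endpoint is fixed at the lowest level by the scale, however large the rise. The study report could then show one event as a mild drug-related AE in one primary-endpoint table and as Grade 3 in the other, with nothing to explain the difference.

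The protocol also treats laboratory events as capable of being severe: Section 4.5 lists a severe laboratory abnormality among the reasons for withdrawal. Section 8.2.3 gives no means of assigning that label. Sections 5.4 (code-break) and 9.2.3 (stoppage) also use the word severe, so its meaning affects conduct as well as display. Some investigators may rate such events higher on their own judgement. With about 7 sites, that would make the rating inconsistent.

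**Working it through.** The plan gives no figure to reproduce here. The first three steps set the texts side by side; the last three size what is left of the stoppage question.

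**1. One event, several rules.** Take a drug-related, symptom-free ALT above 8 and up to 20 × ULN, confirmed on repeat, with a normal baseline.

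| Place | Result |
|---|---|
| Protocol 8.1 | Meets a criterion for stopping drug |
| Protocol 8.2 | An AE if action on drug is required |
| Protocol 8.2.3 | Not discomforting, not incapacitating: Mild |
| SAP 3.6.1, first primary endpoint | Maximum severity Mild |
| SAP 3.6.2, second primary endpoint | Grade 3 |
| Protocol 8.2.4 | AE of special interest |
| Protocol 9.2.3, severe-AE count | Adds 0 |
| Protocol 9.2.3, liver criterion | Counts as 1 |

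**2. Abnormal baseline.** SAP 3.6.2 then grades by multiples of baseline. Exclusion criterion 3 caps ALT and AST at 1.5 × ULN at screening. If the Day 1 baseline stays within that cap, a value above 8 × ULN exceeds 8 / 1.5 = 5.3 times baseline, which is still Grade 3 or higher.

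**3. Other laboratory findings.** A platelet count below 50,000, which stops drug under 8.1, is Grade 3 or 4 in SAP 3.6.2 but Mild under 8.2.3 if there are no symptoms. Creatinine differs: a rise of 0.3 mg/dL stops drug but may be only Grade 1, or ungraded if it stays within the normal range and at or below 1.5 times baseline. The mismatch is therefore clear for ALT, AST and platelets, but not for every drug-stopping finding.

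**4. Stoppage, one group.** The liver criterion in 9.2.3 needs confirmed ALT or AST of 3 × ULN in 3 or more patients in a treatment group, whatever the AE severity. Four cases in one group meet it at the third. With rate p = 0.20 in a group of 12, P(3 or more) = 0.442 and P(4 or more) = 0.205.

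**5. Stoppage, cases spread over groups.** The severe-AE count has no per-group limit, so the two criteria can differ. Place k cases at random over three active groups of 12 and count the allocations with no group at 3 or more.

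- k = 4: patterns 2+2+0 and 2+1+1. 3 × 66 × 66 + 3 × 66 × 12 × 12 = 13,068 + 28,512 = 41,580, out of C(36,4) = 58,905: 70.6%.
- k = 5: 41.6%. k = 6: 14.8%. k = 7: 0%.

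**6. Illustrative rates.** Assume the same rate p in each active group, none on placebo, and every case meeting the liver threshold and counted as severe. Let X be binomial(12, p) and Y binomial(36, p). The liver criterion is met with probability 1 − [1 − P(X ≥ 3)]³, and the severe count would be reached with P(Y ≥ 4). The gap is the probability of 4 or more cases in all with no group at 3.

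| p | Liver criterion | 4 or more of 36 | Gap |
|---|---|---|---|
| 0.05 | 0.058 | 0.104 | 0.061 |
| 0.10 | 0.297 | 0.491 | 0.215 |
| 0.15 | 0.602 | 0.809 | 0.218 |
| 0.20 | 0.826 | 0.948 | 0.125 |
| 0.30 | 0.984 | 0.998 | 0.014 |

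The documents give no ALT event rate at the study doses, so these rows are a range, not an estimate.

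**The case against.** The strongest reply is that intensity and laboratory grade measure different things, so two tables that show both do not contradict each other, and nothing is concealed. Much of this stands. The laboratory grades belong to a primary endpoint themselves. Confirmed Grade 2 or higher ALT is an AE of special interest, reportable within 24 hours and tabulated in SAP 3.6.1. AEs that lead to stopping treatment have their own display, although with dosing on Days 1 and 29 only, this covers rises before the second dose. Protocol 9.2.1 also allows CTCAE grading of safety findings where appropriate, in a section that covers AEs. That sentence leaves room for a link between the scales but does not state one.

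A reader might infer that large ALT rises are hidden from study stoppage. The documents do not support this. Section 9.2.3 has liver, platelet and creatinine criteria that do not use AE severity, and within one group the liver criterion is met before the four-patient count could be. An alarming rise may also be called an important medical event (Section 8.3), which feeds the two-patient criterion for non-cardiovascular serious events. The Safety Review Committee sees unblinded data, includes a gastroenterologist, and works from guidelines rather than automatic triggers.

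A reader might also infer that every ALT above ULN becomes a mild AE, or that Grade 3 values sit exactly two categories too low. Section 8.2 does not make every abnormal value an AE, and the documents contain no mapping of CTCAE grade to mild, moderate and severe against which to count categories.

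**Conclusion.** The point holds as an inconsistency in how the first primary endpoint describes laboratory toxicity. As written, a symptom-free, drug-related ALT or AST above 8 × ULN is Mild there and Grade 3 in the second primary endpoint (Grade 4 above 20 × ULN), and no text relates the two scales. This rests on a literal reading of 8.2.3 and on the investigator judging the event drug-related. How often it would occur cannot be said from the documents.

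For stoppage the consequence is limited to two cases: four to six liver cases spread so that no group has three, and laboratory AEs with no criterion of their own in 9.2.3, such as creatine kinase. In the illustration the first has probability 0.014 to 0.218 for p from 0.05 to 0.30. Those figures assume equal rates across active groups; a dose-related effect would concentrate cases and make the liver criterion more likely to catch them. It is worth correcting because the misplaced category falls in a primary endpoint and concerns the known signal, but it is not a failure of safety oversight.

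**What to change.** In SAP 3.6.1, for AEs that are laboratory findings with a CTCAE Version 5.0 grade in SAP 3.6.2, report the first primary endpoint's maximum severity by that grade, or by a stated mapping of it to mild, moderate and severe. Use the worst graded value during the event, including unscheduled repeats. Keep the functional scale for clinical AEs and for laboratory findings without a grade in the table. Say so in Protocol 8.2.3 and in the eCRF guidance.

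Separately, the sponsor should reconcile which scale the word severe refers to in Protocol 4.5, 5.4 and 9.2.3. The reporting change should not silently alter how the code-break or stoppage provisions work.

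The cost is a sentence in 8.2.3, eCRF guidance, and one SAP derivation with a rule linking AE records to laboratory values. The count of severe drug-related AEs may look less favourable. A few drug-stopping findings stay on the functional scale because the SAP table does not grade them: haematuria, albuminuria, and small creatinine rises within the normal range.
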